4.2 Secondary Safety Endpoints

Safety and tolerability will be assessed through AEs, AEs leading to discontinuation, SAEs, deaths and laboratory abnormalities in combination therapy during the treatment period plus 30 days of follow-up. AEs will be graded according to NCI CTCAE v4.03.

Triplicate measurements of each serial ECG will be used to obtain an average value for each time point. Baseline will be defined as the time point prior to dosing on the first day of Cycle 1. All available non-missing values of ECG parameters should be used in the analyses. However:

- if QTcF is missing and RR in seconds is available, then QTcF will be calculated as $QTcF = QT / RR(1/3)$;
- if both QTcF and RR in seconds are missing, then QTcF will be calculated as $QTcF = QT / (60 / HR)(1/3)$.

The primary ECG endpoint is $\Delta QTcF$, the change from baseline in QTcF, the QT interval normalized using Fridericia's heart rate correction. Other endpoints include QTcF, QT, QRS, PR, HR (heart rate), and QTcB as well as ΔQT , ΔQRS , ΔPR , ΔHR (heart rate), $\Delta QTcB$, the associated changes from baseline. (Note: QTcB is the QT interval normalized using Bazett's heart rate correction.)

4.3 Secondary Pharmacokinetic Endpoints

The following pharmacokinetic (PK) parameters will be determined, whenever data permit:

C _{max}	Maximum observed serum concentration
C _{trough}	Trough observed serum concentration
T _{max}	Time of maximum observed ulocuplumab serum concentration

AUC(0-T)	Area under the ulocuplumab concentration-time curve from time zero to the last quantifiable concentration (calculated by log- and linear-trapezoidal summation)
AUC(TAU)	Area under the ulocuplumab concentration-time curve in one dosing interval
AUC(INF)	Area under the ulocuplumab concentration-time curve from time zero to infinity (calculated by summing AUC(0-T) and the extrapolated area, computed by the quotient C_{last}/λ_z)
T-HALF	Elimination half-life, determined as $0.693/\lambda_z$
CLT	Total body clearance of ulocuplumab (calculated by dividing the total dose of ulocuplumab by its corresponding AUC(INF) value)
V _{ss}	Volume of distribution at steady state

AUC from the time of dosing extrapolated to infinity (AUC[INF]) after first dosing, CLT, V_{ss} and T-HALF will be calculated when feasible. Individual subject PK parameter values will be derived by non-compartmental methods by a validated PK analysis program. Actual times will be used for the analyses.

4.4 Secondary Immunogenicity Endpoints

Immunogenicity is measured by the incidence of anti-drug antibodies for ulocuplumab. Based on the recommendation from BMS Immunogenicity Council, White Paper on Assessment and Reporting of the Clinical Immunogenicity of Therapeutic Proteins and Peptides - Harmonized Terminology and Tactical Recommendations by Shankar et al,¹ and the FDA Guidance for Industry Immunogenicity Assessment for Therapeutic Protein Products,² the following definitions of ADA status will be applied:

- Baseline ADA-positive sample: ADA is detected in the last sample before initiation of treatment
- ADA-positive sample: after initiation of treatment, (1) an ADA detected (positive seroconversion) sample in a subject for whom ADA is not detected at baseline, or (2) an ADA detected sample with ADA titer to be at least 4-fold or greater (\geq) than baseline positive titer
- ADA-negative sample: After initiation of treatment, ADA not positive sample relative to baseline

5 SAMPLE SIZE AND POWER

The size of the study is not based on testing a formal statistical hypothesis. For Phase 2 (expansion cohort), a sample size of 40 subjects per treatment group will allow estimation of the response rate with the following degree of precision, where response is defined by complete remission (CR/CRi). A response rate of 0.6 will be estimated with a 95% exact confidence interval (CI) of 0.43 - 0.75. If the response rate is 0.45, then the associated 95% CI will be 0.29 - 0.62.

6 STUDY PERIODS, TREATMENT REGIMENS AND POPULATIONS FOR ANALYSES

6.1 Study Periods

Within each phase, this study consists of three analysis periods: pre-treatment, on-treatment, and post-treatment.

- The pre-treatment period extends from the time of signing the informed consent form to prior to the first dose of study medication.
- The on-treatment period starts at the time of the first dose of study medication and ends 30 days following the last day of dosing (if a subject discontinues study medication).
- The post-treatment period begins after 30 days following the last day of dosing.

6.2 Treatment Regimens

Unless otherwise specified, analyses will be performed by Phase 2 treatment arm:

- 1) ulocuplumab 800 mg in combination with LDAC 20 mg BID;
- 2) ulocuplumab 1000 mg in combination with LDAC 20 mg BID;
- 3) LDAC 20 mg BID alone.

Demographic and baseline characteristics, as well as (Phase 2) efficacy, will be summarized (in all randomized subjects) by treatment arm as randomized (per IWRS). Safety and exposure will be summarized (in all treated subjects) by treatment arm as treated. (In general, 'as treated' will be the same as 'as randomized'. However, if a subject received an incorrect drug for the entire period of treatment, the subject will be summarized according to the incorrect drug that the subject actually received.)

6.3 Populations for Analyses

The following populations will be defined:

- *All Enrolled Subjects*: All subjects who signed an informed consent form and were registered into the IWRS. Subject disposition will be tabulated using this dataset.
- *All Randomized Subjects* (expansion cohort only): All subjects who signed an informed consent form and were randomized to either ulocuplumab 800 mg or 1000 mg in combination with LDAC or to LDAC alone. Demographic and baseline characteristics, as well as Phase 2 efficacy, will be summarized in all randomized subjects.
- *Response-evaluable subjects* (around 60 subjects at time of Interim Meeting #1): All randomized subjects who have opportunity to complete at least 2 cycles of treatment and

follow-up during the expansion phase. This will be the basis of some Phase 2 efficacy analyses in DMC Interim #2.

- *All Treated Subjects*: All subjects who received at least one dose of any study medication (ulocuplumab in the combination arm and LDAC in the LDAC only arm). Safety and exposure (as well as Phase 1 efficacy), will be summarized in all treated subjects.
- *PK Subjects*: All treated subjects who received at least one dose of ulocuplumab and have evaluable PK data.
- *Immunogenicity Subjects*: All subjects treated with ulocuplumab who have baseline and at least one post-baseline immunogenicity assessment.

7 STATISTICAL ANALYSES

7.1 General Methods

Unless otherwise specified, the following are analyses of the expansion cohort, by treatment group, and will be produced for both DMC interim #2 and final analyses. A subset of these analyses will support DMC interim #1 and DMC interim #3 (SAE); further details will be given in the DPP and DMC Charter.

In general, continuous variables will be summarized using descriptive statistics, i.e. mean, standard deviation, median, minimum and maximum values. Geometric mean and coefficient of variation will also be presented for sample serum concentration-time data and PK parameters. Categorical variables will be summarized by frequencies and percentages. Percentages will be rounded and may not always add up to 100.

7.2 Study Conduct

7.2.1 Accrual

- Accrual summary by country and site (numbers enrolled, randomized).
- Accrual listing (with informed consent date, country, investigational site, randomization date)

7.2.2 Relevant Protocol Deviations

The following relevant deviations will be summarized:

- Subject not AML (de novo or secondary) with blasts $\geq 20\%$;
 - ECOG > 3 ;
 - screening WBC $\geq 100,000$ mL;
 - screening creatinine > 2 mg/dL;
 - screening AST or ALT > 3 x ULN;
 - screening total bilirubin > 2 mg/dL;
 - prior surgery within 4 weeks of first ulocuplumab dose;
 - prior new investigational therapy within 4 weeks prior to first ulocuplumab dose;
 - prior AML therapy (other than hydroxurea);
 - concomitant use of AML systemic therapy;
 - on-study use of new investigational therapy.
- Relevant deviations summary
 - Relevant deviations listing

7.3 Study Population

7.3.1 Subject Disposition

The following will be provided:

- Pre-randomized subject status summary (with number of subjects enrolled, randomized, not randomized - with reason)
- Pre-treated subject status listing (with randomization date, treated, reason not treated)
- End of treatment period subject status summary (numbers continuing/not continuing in treatment period - with reason, continuing/not continuing in study - with reason)
 - For LDAC-alone subjects who enter a period of ulocuplumab treatment, the status of this added treatment will similarly be summarized:
 - ◆ End of added ulocuplumab period subject status summary
- End of treatment period subject status listing (continuing in treatment period, reason not continuing, continuing in study)
- End of follow-up subject status summary (numbers continuing/not continuing to be followed - with reason)
- End of follow-up subject status listing (continuing to be followed, not continuing - with reason)

7.3.2 Demographics and Other Baseline Characteristics

7.3.2.1 Demographics and Baseline Disease Characteristics

The following will be provided:

- Demographic characteristics summary (age [descriptive statistics], age categorization [<70 , ≥ 70], gender, race)
- Disease characteristics summary (ECOG performance status, Hematopoietic Cell Transplant-comorbidity index [HCT-CI: 0-4, 5-9, 15-19, 20-24, 25+])

7.3.2.2 Prior Cancer Therapy

- Prior radiotherapy summary (yes/no)
- Prior systemic cancer therapy summary (yes/no, number of regimens)
- Prior cancer therapy listing

7.3.2.3 Physical Measurements

- Physical measurements summary (descriptive statistics for body weight, height and body mass index)
- Physical measurements listing (body weight, height, body mass index)

7.4 Extent of Exposure

7.4.1 Study Therapy

Duration of therapy (in days) is defined as date of last dose of therapy - date of first dose + 1. Cumulative dose (mg) is the sum of all actual doses that a subject received. Relative dose intensity (%) is defined as dose intensity / planned dose intensity x 100, where dose intensity (mg/day) = cumulative dose/ duration on assigned dose level in days.

Duration on assigned dose level will be calculated as follows:

- $TD = \text{last dose date of Ulocuplumab} - \text{first dose date of Ulocuplumab} + 1$
- If last non-zero dose is at Cycle 1 or Cycle 2:
 - 1) if the last dose is first scheduled dose of that cycle, then duration on assigned dose level = $TD + 7$;
 - 2) If last dose is second scheduled dose of that cycle, then duration on assigned dose level = $TD + 7$;
 - 3) If last dose is third (last) scheduled dose of that cycle, then duration on assigned dose level = $TD + 14$.
- If last non-zero dose is at Cycle 3 or later:
 - 1) if the last dose is first scheduled dose of that cycle, time on treatment = $TD + 7$;
 - 2) If last dose is second scheduled dose of that cycle, then time on treatment = $TD + 21$.

Planned dose intensity will be calculated as follows:

- Cycle 1 or Cycle 2: $\text{Planned Dose Intensity} = (\text{Assigned Dose} * 3) / 28 \text{ days}$
- Cycle 3 or later $\text{Planned Dose Intensity} = (\text{Assigned Dose} * 2) / 28 \text{ days}$
-

The following will be provided:

- Duration of ulocuplumab summary (1-28, 29-56, 57-84, 85-168, ≥ 169 ; median, min-max)
- Duration of LDAC summary (1-28, 29-56, 57-84, 85-168, ≥ 169 ; median, min-max)
- Number of ulocuplumab infusions summary (1, 2, 3, 4, 5, 6, 7, 8, 9, 10, >10)
- Cumulative dose summary (descriptive statistics [mg])
- Relative dose intensity summary ($<60\%$; $60-<80\%$; $80-<90\%$; $90-<100\%$; $\geq 100\%$)
- Extent of exposure listing (with duration of therapy, cumulative dose, relative dose intensity)

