4.6.1.2 Dose Modifications, Infusion Delays and Missed Doses

No subject will be permitted dose modifications of ulocuplumab and LDAC during Cycle 1. After Cycle 1, if the dose of ulocuplumab or LDAC is interrupted or discontinued, the treatment with the other drug may continue as scheduled. Each cycle is 28 days. Missed doses should be skipped, not delayed, if not given within the allowed window. Please consult the BMS Medical Monitor for any questions regarding dose interruption or study therapy discontinuation.

Ulocuplumab:

The study allows dose delays of ulocuplumab but does not allow dose reductions or escalations throughout the treatment period. Dose delays of ulocuplumab are not permitted during Cycle 1.

Criteria to start a new cycle:

- After Cycle 1, every effort should be made to give the first dose of ulocuplumab and LDAC in Cycle 2 within 7 days of the end of the previous cycle in order to maximize dose intensity. Dose delays up to a maximum of 28 days are allowable for grade 3 or 4 non-hematologic toxicities, with resumption of dosing when resolved to grade 1 or less. This does not include situations when the subject's marrow has not yet recovered from effects of chemotherapy from a previous cycle. A dose delay of up to a maximum of 42 days is allowable for prolonged myelosuppression defined by ANC $\leq 500/\mu\text{L}$ or platelet count $\leq 10 \times 10^9/\text{L}$ in a normal bone marrow with $\leq 5\%$ blasts and no evidence of disease or dysplasia .
- At Cycle 3 and beyond, dose delay for recovery from myelosuppression (or other AE) up to a maximum of 56 days is allowed for grade 3 or 4 non-hematologic toxicities, or prolonged myelosuppression as defined above.

Once a treatment cycle is begun:

- For Cycles 1 and 2, a window of -1 to +3 days is permitted for ulocuplumab administration on Days 8 and 15.
- Beginning with Cycle 3 and beyond, a window of -1 to +7 days is permitted for ulocuplumab administration on Day 8.
- Infusions of ulocuplumab that cannot be administered in that window period will be considered a missed dose, and the subject should come in for their next, regularly scheduled visit relative to Day 1 of the next cycle.

A subject should be discontinued from ulocuplumab if they do not receive a dose within 56 days of the last ulocuplumab dose.

Table 4.6.1.2-1: Dose Delay and Discontinuation Criteria for Ulocuplumab-related Adverse Events

Adverse Event	Action

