7.4.2 Modifications of Study Therapy

- Dose change summary for ulocuplumab (numbers with dose modification, dose interruption - with reason, dose delay - with reason, dose omission, dose discontinuation)

Dose change summary for LDAC?

- Dose change listing

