8 CONVENTIONS

Safety data will be handled according to the BMS safety data conventions (described in ‘Analysis of Safety Data - Reference to CT SOP 109’). Further information regarding conventions is given in the DPP.

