9 CONTENT OF REPORTS

Refer to the DPP for details of the outputs that will be produced.

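### Relative dose intensity in SAP 7.4.1 counts one day too many, and the documents give no rule for combining its two planned rates

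*SAP*

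**What the plan says.** SAP 7.4.1 says that "Relative dose intensity (%) is defined as dose intensity / planned dose intensity x 100". The numerator of that ratio is given by the clause "where dose intensity (mg/day) = cumulative dose/ duration on assigned dose level in days". Cumulative dose is the sum of all doses actually received.

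Duration is built from TD, defined as last ulocuplumab dose date minus first dose date plus 1. An interval is then added according to which scheduled dose came last:

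- Cycle 1 or 2, first or second dose: TD + 7.
- Cycle 1 or 2, third dose: "If last dose is third (last) scheduled dose of that cycle, then duration on assigned dose level" is TD + 14.
- Cycle 3 or later, first dose: TD + 7.
- Cycle 3 or later, second dose: TD + 21.

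Planned dose intensity is 3 × assigned dose / 28 days for Cycle 1 or 2, and 2 × assigned dose / 28 days for Cycle 3 or later. Results are tabulated in bands cut at 60, 80, 90 and 100%, and are also listed.

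The SAP points to a Data Presentation Plan (DPP) that was not available here. Section 8 says "Further information regarding conventions is given in the DPP" and Section 9 says "Refer to the DPP for details of the outputs that will be produced".

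**The concern.** **(a) Extra day.** TD is an inclusive count, so it already contains the last dose day. Adding the whole interval to the next dose counts that day twice. The duration then disagrees with the 28-day cycle in the same section's planned rates.

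**(b) No combining rule.** Cumulative dose and duration span the whole course, but each printed planned rate applies to only part of it. For a subject who reaches Cycle 3, neither rate alone is the plan, and no weighting is stated.

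**(c) Mid-cycle stops.** In Cycles 1-2, a subject whose last dose is the first or second of the cycle is credited 7 days for it. That is compared with a rate averaged over 28 days, which includes the dose-free stretch after Day 15.

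At stake is whether the table can be read at face value. Full adherence can appear as under-dosing, missed infusions can be hidden, and two programmers following the SAP could produce different tables.

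**Working it through.** **Inputs.** The formulas are those of SAP 7.4.1. Dosing days are those of Protocol 4.4 and 4.6: Days 1, 8 and 15 in Cycles 1-2, Days 1 and 8 from Cycle 3, with 28-day cycles. The assigned dose cancels, so RDI = (doses / duration) / (3/28 or 2/28), the same for 800 mg and 1000 mg. The SAP prints no RDI value, so the benchmark is its own 28-day cycle.

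**(a) Extra day, nominal dosing.**

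- One full cycle: TD = 15, + 14 = 29 days, not 28. RDI = (3/29)/(3/28) = 96.6%.
- Two full cycles: TD = 43, + 14 = 57 days, not 56. RDI = (6/57)/(3/28) = 98.2%.
- Three full cycles: TD = 64, + 21 = 85 days, not 84.

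The excess is exactly one day in all five branches.

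**(b) Choice of planned rate, nominal dosing.**

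| Last dose | Doses / days | At 2/28 | At 3/28 |
|---|---|---|---|
| Cycle 3 Day 1 | 7/64 | 153.1% | 102.1% |
| Cycle 3 complete | 8/85 | 131.8% | 87.8% |
| Cycle 4 Day 1 | 9/92 | 137.0% | 91.3% |
| Cycle 6 complete | 14/169 | 116.0% | 77.3% |
| Cycle 12 complete | 26/337 | 108.0% | 72.0% |

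From Cycle 3 Day 8 through Cycle 12, every on-schedule stop is at least 108.0% at 2/28 and at most 91.3% at 3/28, so the choice always changes the band. Cycle 3 Day 1 is ≥100% at both.

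A subject given 8 of 10 infusions over four cycles, including the last, scores (8/113)/(2/28) = 99.1% or (8/113)/(3/28) = 66.1%. The share actually given is 80%.

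With a cycle-weighted plan, only the extra day remains: 84/85 = 98.8% at three cycles and 168/169 = 99.4% at six.

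**(c) Mid-cycle stops.**

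- Cycle 1, first dose: (1/8)/(3/28) = 116.7%.
- Cycle 1, second dose: (2/15)/(3/28) = 124.4%.
- Cycle 2, first dose: (4/36)/(3/28) = 103.7%. After a 2-day accumulated delay, (4/38)/(3/28) = 98.2%.
- Cycle 2, second dose: (5/43)/(3/28) = 108.5%. After a 4-day accumulated delay, (5/47)/(3/28) = 99.3%.

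Protocol 4.6.1.2 states "For Cycles 1 and 2, a window of -1 to +3 days is permitted for ulocuplumab administration on Days 8 and 15". Across that window the Cycle 1 second-dose value runs from (2/14)/(3/28) = 133.3% to (2/18)/(3/28) = 103.7%.

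Removing only the extra day makes both nominal Cycle 1 values larger: (1/7)/(3/28) = (2/14)/(3/28) = 133.3%.

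**The case against.** **The rule may exist elsewhere.** The DPP could hold it, and in the copy read an empty bullet follows the two planned rates, which may be lost text. This stands as a limit on (b), which claims only that the available documents state no rule. It does not touch (a).

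**The two rates can be read as per-cycle plans.** That gives a weighted denominator, and the large contrasts in (b) disappear. Another natural reading takes the rate of the last dose's cycle, matching the duration branches; it gives 131.8% at three cycles. The SAP chooses neither, so the contrasts measure the ambiguity rather than a prescribed error.

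**The extra day does not bind everyone.** With Day 15 given one day early, as permitted, Cycle 1 has TD 14 + 14 = 28 days and Cycle 2 has 42 + 14 = 56. Both score exactly 100%. Part (a) is therefore a statement about nominal days.

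**The weight is small.** On nominal days, (a) costs 3.4 points after one cycle and 1.8 after two. Once (a) is fixed, (c) alters listed values for on-schedule subjects in Cycles 1-2 but not their band, since they are ≥100% either way. The study is exploratory and non-comparative. Infusion counts and cumulative dose are reported as well, and SAP 7.4.2 plans a "Dose change summary for ulocuplumab (numbers with dose modification, dose interruption - with reason, dose delay - with reason". All of this is right, and it confines the point to one descriptive summary.

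**Conclusion.** The concern holds. Part (a) is an arithmetic error in the printed text: full on-schedule adherence for one or two cycles is reported as 96.6% or 98.2%, in the 90-<100% band. Part (b) is a gap in the available documents with a larger possible effect: the same compliant six-cycle subject is 116.0%, 99.4% or 77.3% depending on an unstated choice. Part (c) is a mismatch that inflates listed values for early stoppers and grows if (a) is corrected alone.

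These figures assume the protocol's dosing days, dosing on nominal days unless stated, and that the term time on treatment in the Cycle 3 branches means the same as duration on assigned dose level. The effect is limited to the RDI table and listing. The primary endpoint is unaffected.

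A separate inconsistency does not alter the figures. SAP 2.2 gives Days 1 and 15 after Cycle 2 for the combination arms. Protocol 4.4 and 4.6, and SAP 2.2's own note on adding ulocuplumab to LDAC alone, give Days 1 and 8. The 7- and 21-day intervals fit the latter. These passages must be reconciled.

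**What to change.** In SAP 7.4.1:

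1. Set duration = last dose date − first dose date + the interval already printed (7, 14 or 21), without the extra 1.
2. Set planned intensity = (infusions scheduled from first dose through the last scheduled dose reached × assigned dose) / (nominal days through the end of that dose's interval).

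On nominal days this gives 100% at every stopping point, and (8/112)/(10/112) = 80% for 8 of 10 infusions when the final scheduled dose was given. Delays still count. Protocol 4.6.1.2 says "A dose delay of up to a maximum of 42 days is allowable for prolonged myelosuppression"; four full cycles with a 42-day delay before Cycle 2 give (10/154)/(10/112) = 72.7%.

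State two limits in the SAP:

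- In-window dosing can still move early stoppers off 100%. For a last dose at Cycle 1 Day 8, one day early gives 14/13 = 107.7% and three days late gives 14/17 = 82.4%. The latter is a change of band from the current 103.7%, with no dose missed.
- Doses missed after the last one received are not counted. Eight infusions with the last at Cycle 4 Day 1 give (8/91)/(9/91) = 88.9%, not 80%.

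If the DPP already holds a combining rule, move it into SAP 7.4.1. Reconcile SAP 2.2 with Protocol 4.4 and 4.6, and recheck the intervals if the schedule text changes. The cost is SAP wording and one derivation, with no new data.

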7.4.2 Modifications of Study Therapy

- Dose change summary for ulocuplumab (numbers with dose modification, dose interruption - with reason, dose delay - with reason, dose omission, dose discontinuation)

Dose change summary for LDAC?

- Dose change listing

7.4.3 Concomitant Medications

Concomitant medications (taken up to 30 days following the last dose of study therapy) will be tabulated and listed.

- Non-study medications summary (number of subjects by WHO anatomic class, therapeutic class and generic name)
- Non-study medications listing

